Specific Aim 5: Explore modifiable factors that may impact physical activity, as assessed with step activity monitors, including comorbidities, balance-confidence, fatigue, sleep disturbance, balance, functional lower extremity strength, functional mobility and agility among adults with (n=20) and without a unilateral below-the-knee amputation (n=20).

Hypotheses: For both adults with and without a below-the-knee amputation (after controlling for covariates):

H5a: Comorbidities: Average daily step counts will be significantly lower for adults with greater comorbidity burden, as assessed with the Cumulative Illness Rating Scale.

H5b: Balance-Confidence: Average daily step counts will be significantly lower for adults who have lower balance-confidence per the Activities-Specific Balance Confidence Scale.

H5c: Fatigue: Average daily step counts will be significantly lower for adults who indicate fatigue on the PROMIS-29, as compared to those who do not indicate fatigue.

H5d: Sleep Disturbance: Average daily step counts will be significantly lower in adults who indicate sleep disturbance on the PROMIS-29, as compared to those who do not indicate sleep disturbance.

H5e: Balance: Average daily step counts will be significantly lower in adults with decreased Functional Reach Test distance and adults who are unable to maintain balance for 30 seconds during m-CTSIB conditions 3 and 4 (foam, eyes open and foam, eyes closed).

H5f: Functional Lower Extremity Strength: Average daily step counts will be significantly lower in adults with decreased lower extremity functional strength, defined as slower 5 Times Repeated Chair Rise times.

H5g: Functional Mobility: Average daily step counts will be significantly lower in adults with decreased functional mobility, defined as increased L-test times.

H5h: Agility: Average daily step counts will be significantly lower in adults with worse agility as indicated by slower Four Square Step Test times and Figure-of-8 Walk test times.

Specific Aim 6: Explore the relationship between gait asymmetry, as quantified by spatio-temporal and 3D kinematic parameters (e.g. cadence, stance and swing time, step length, and joint position), and energy expenditure among inactive adults with a single, below-the-knee amputation (n=20) during treadmill walking at self-selected and fast walking speeds.

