Hypothesis: Energy expenditure will be greater among inactive adults with a single, below-the knee amputation who demonstrate greater side-to-side differences in walking pattern during treadmill walking at both self-selected and fast walking speeds ($p<0.05$).

Specific Aim 7: Compare side-to-side differences in walking pattern (e.g. speed, step length, and joint position) between inactive adults with a single, below-the-knee amputation (n=20) and age-matched controls (n=20) during over-ground and treadmill walking using the APDM Mobility Lab software.

Hypothesis: For both over-ground and treadmill walking conditions, inactive adults with a single, below-the knee amputation will demonstrate greater side-to-side differences in walking pattern compared to age-matched controls ($p<0.05$).

Specific Aim 8: Explore the relationship between inspiratory muscle endurance, as quantified by an individual's sustained maximal inspiratory pressure (SMIP), and energy expenditure among inactive adults with a single, below-the-knee amputation (n=20) during treadmill walking at self-selected and fast walking speeds.

Hypothesis: Energy expenditure will be greater among inactive adults with a single, below-the knee amputation who demonstrate decreased SMIP values (p<0.05).

Specific Aim 9: Compare differences in inspiratory muscle endurance (measured by sustained maximal inspiratory pressure, or SMIP) between inactive adults with a single, below-the-knee amputation (n=20) and age-matched controls (n=20) using the PrO₂ device.

Hypothesis: Inactive adults with a single, below-the knee amputation will demonstrate decreased SMIP values compared to age-matched controls (p<0.05).

Specific Aim 10: Compare differences in inspiratory muscle endurance (measured by sustained maximal inspiratory pressure, or SMIP) between inactive adults with a single, below-the-knee amputation who have low back pain compared to those who do not report pain.

Hypothesis: Inactive adults with a single, below-the knee amputation who experience low back pain will demonstrate decreased SMIP values compared to individuals with a single, below-the-knee amputation who do not have pain (p<0.05).

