Specific Aim 1: To determine reliability, intra-class correlation coefficients (ICCs) with 95% confidence intervals (CIs) will be calculated to evaluate test-retest reliability of physical activity

questionnaires. To evaluate validity between the self-report questionnaire data and activity-monitor obtained data that is continuous (e.g. steps/day, total activity in minutes/day), we will use ICCs with 95% CIs. We will quantify the relationship between the self-report data and activity-monitor data using Spearman's correlation coefficients. Interpretation will be as follows: $p \leq .25$ =weak correlation, $p=.26\text{--}.49$ =low correlation, $p=.50\text{--}.69$ =moderate correlation, $p \geq .70$ =high correlation.

Specific Aim 2: We will use receiver operating characteristic (ROC) curves to determine the minimal speed and cadence that corresponds to an oxygen consumption value of 10.5 mL/kg/min (i.e. 3.0 METs), as this has been identified by the World Health Organization as 'moderate intensity' activity.¹⁰

Specific Aims 3 and 6-10: We will use a MANOVA/MANCOVA to evaluate between-group differences with follow-up ANOVAs/ANCOVAs as appropriate ($p \leq 0.05$).

Specific Aims 4/5: Regression models will be used to explore relationships between energy expenditure (or average daily step counts) and each of the modifiable factors of interest, while controlling for relevant non-modifiable covariates, e.g. age, residual limb length.

Reported

Dissemination of results will occur through conference presentations and manuscript publications in peer-reviewed journals.

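### Aims 6 and 8 ask how a measured quantity relates to energy expenditure within one amputee group, but the plan assigns them a between-group MANOVA/MANCOVA with no groups or cut-offs defined

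*Combined protocol and SAP*

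**What the plan says.** The analysis text in Section 10 (DATA) covers six aims in one sentence: "Specific Aims 3 and 6-10: We will use a MANOVA/MANCOVA to evaluate between-group differences with follow-up ANOVAs/ANCOVAs as appropriate", with a 0.05 threshold.

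Section 5 (Research Abstract) sets out what Aims 6 and 8 ask:

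- **Aim 6** is to "Explore the relationship between gait asymmetry, as quantified by spatio-temporal and 3D kinematic parameters" and energy expenditure. Its hypothesis is that energy expenditure will be higher in those "who demonstrate greater side-to-side differences in walking pattern during treadmill walking at both self-selected and fast walking speeds".
- **Aim 8** is to "Explore the relationship between inspiratory muscle endurance, as quantified by an individual's sustained maximal inspiratory pressure (SMIP), and energy expenditure among inactive adults". Its hypothesis reads "Energy expenditure will be greater among inactive adults with a single, below-the knee amputation who demonstrate decreased SMIP values".
- **Population.** Both aims are confined to the amputee participants and share the phrase "energy expenditure among inactive adults with a single, below-the-knee amputation (n=20) during treadmill walking at self-selected and fast walking speeds".

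The next line of Section 10, for Aims 4 and 5, names a different method: "Regression models will be used to explore relationships between energy expenditure (or average daily step counts) and each of the modifiable factors", with control for covariates such as age and residual limb length.

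**The concern.** A test of differences between groups needs a grouping factor. Aims 6 and 8 have one group and a measured predictor, so the stated method leaves open what will be compared with what. Two analyses are possible: a model that keeps asymmetry or SMIP continuous, or a comparison of high and low groups formed by some cut-off. The plan does not choose between them.

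Both hypotheses are to be judged at p<0.05. If groups are formed, the cut-off could be picked after the data are seen, and the p-value would then lose its stated meaning. Even a cut-off fixed in advance would discard information in a sample of about 20.

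**Working it through.** **1. Each aim under the MANOVA/MANCOVA line, set against its wording in Section 5**

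| Aim | Participants | Question | Groups named? |
|---|---|---|---|
| 3 | Amputee and control | Difference in energy expenditure | Yes |
| 6 | Amputee only, n=20 | Relation of gait asymmetry to energy expenditure | No |
| 7 | Amputee and control | Difference in asymmetry | Yes |
| 8 | Amputee only, n=20 | Relation of SMIP to energy expenditure | No |
| 9 | Amputee and control | Difference in SMIP | Yes |
| 10 | Amputee only | Difference in SMIP by low back pain | Yes |

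Aim 10 shows that the plan names groups within the amputee sample when it wants them: "between inactive adults with a single, below-the-knee amputation who have low back pain compared to those who do not report pain".

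**2. Search for a grouping rule.** The hypotheses for Aims 6 and 8 speak of greater asymmetry and lower SMIP, with no threshold, median split or reference value. The Section 6 (Procedures) text on inspiratory muscle testing and on the gait sensors gives none either. The SMIP text says these measures serve to relate breathing endurance to oxygen consumption, which is the language of association. The plan can state a threshold when it wants one: H5e uses failure to hold balance for 30 seconds.

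**3. The matching method is already in the plan.** Aims 4 and 5 relate measured factors to an outcome, and Aim 4 has the same outcome as Aims 6 and 8. They are assigned regression.

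**4. Illustration of what a split would cost.** The documents give no power calculation or expected correlation for these aims, so there is no stated figure to reproduce. Assumptions: n=20, two-sided 0.05, one outcome, bivariate normal data, correlation r assumed. The continuous analysis tests t = r̂·√[(n−2)/(1−r̂²)] on n−2 = 18 degrees of freedom. The split analysis is a two-sample t-test. Simulated power:

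| Assumed r | Continuous | Median split (10 vs 10) | Lowest quarter (5 vs 15) |
|---|---|---|---|
| 0 (type I error) | 0.049 | 0.049 | 0.049 |
| 0.3 | 0.255 | 0.171 | 0.147 |
| 0.4 | 0.431 | 0.277 | 0.233 |
| 0.5 | 0.642 | 0.424 | 0.355 |
| 0.6 | 0.836 | 0.600 | 0.504 |

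The first two power columns use 200,000 replicates and the last uses 40,000. Simulation standard error is at most √(0.25/40,000) = 0.0025. For r from 0.3 to 0.6, the median split loses 0.255−0.171 = 0.084 up to 0.836−0.600 = 0.236, that is, 8 to 24 percentage points.

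Two hand checks agree with the table:

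- Continuous, r=0.5, by Fisher's z: atanh(0.5)·√17 = 0.5493 × 4.1231 = 2.265; 2.265 − 1.960 = 0.305; Φ(0.305) ≈ 0.62, against 0.642 simulated.
- A median split of a normal predictor shrinks r by about √(2/π) = 0.798. So r=0.5 acts like 0.5 × 0.798 ≈ 0.40, where continuous power is 0.431, against 0.424 simulated.

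**5. Two covariates in the model** (20 − 4 = 16 residual degrees of freedom; 40,000 replicates). Continuous against median split: 0.224 vs 0.152 at r=0.3, 0.392 vs 0.248 at 0.4, 0.593 vs 0.382 at 0.5, 0.793 vs 0.545 at 0.6. These covariates were independent of the predictor, so the figures show little more than the lost degrees of freedom. Real covariates could raise or lower power.

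**6. Smallest correlation detectable with 80% power, continuous predictor:** tanh[(1.960 + 0.842)/√(n−3)]. For n=20, tanh(2.802/4.123) = tanh(0.680) ≈ 0.59. For the 22 amputees that Section 6 plans to recruit, tanh(2.802/4.359) = tanh(0.643) ≈ 0.57.

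**The case against.** The strongest defence is that a MANCOVA can carry asymmetry or SMIP as a continuous covariate. The test of that slope comes from the same general linear model as a regression, and it can take the two treadmill speeds as joint outcomes. This is correct, and it means the analysis is easily repaired. It does not rescue the sentence as written, which gives the purpose as comparing groups and assigns asymmetry and SMIP no role as covariates. The phrase allowing methods to be used as appropriate attaches to the follow-up ANOVAs/ANCOVAs, not to the choice of main analysis.

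A second defence is that the hypotheses imply high and low groups. The cut-offs would then be missing, so the gap remains.

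A third is that both aims are worded as exploration in a small cross-sectional study, and no treatment or safety decision rests on them. That limits the seriousness. However, Section 5 gives its explicit exploratory caveat to Aims 4 and 5 only, and Aims 6 and 8 each carry a p<0.05 criterion.

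Three further points stand:

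- The power comparison sets regression against a split that the plan never proposes, so it shows what is at stake and does not measure a loss in this study.
- Section 6 already names residual limb length, foot type and suspension system as factors to control when energy expenditure is analysed. Any covariate choice must deal with these.
- Treadmill stages are set as percentages of each person's own speed, and the pilot mean self-selected speeds were 0.88 m/sec (K3) and 1.16 m/sec (K4). Participants are therefore tested at different absolute speeds, which could confound the slope.

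**Conclusion.** The concern holds. The stated analysis does not match the question in Aims 6 and 8, and this follows from the text alone without any assumption. It is a wrong assignment, probably because the range 6-10 took in two aims that belong with Aims 4 and 5. It is not merely a missing detail.

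The size of the consequence depends on what the investigators would do, which is not stated. Under the assumptions above, splitting at the median would cost 8 to 24 percentage points of power, and a 5 vs 15 split would cost more. Power stays below 65% for r of 0.5 or less even with a continuous predictor. A non-significant result would therefore say little, and the estimated slope with its interval is more informative than the p-value. The point should be corrected before analysis; it does not threaten the study as a whole.

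**What to change.** In Section 10, limit the MANOVA/MANCOVA line to Aims 3, 7, 9 and 10, and extend the regression line to Aims 4, 5, 6 and 8. For Aims 6 and 8, add:

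- asymmetry or SMIP enters as a continuous predictor;
- the main result is the slope with its 95% confidence interval at each treadmill speed (self-selected and fast), allowing for repeated measures if the two speeds are modelled together;
- a small covariate set fixed in advance, for example age and residual limb length, with a sentence on whether foot type and suspension are included, since about 20 participants cannot support many terms;
- whether the main slope is adjusted for absolute walking speed, with the other version as a sensitivity analysis;
- for Aim 6, one or two asymmetry indices named in advance, because the gait system yields many.

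If groups really are intended, stating the cut-offs in advance would also remove the contradiction, at the price in power shown above.

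The core correction is one or two lines, and the supporting details add a few more. Data collection and sample size do not change.

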11. CONFIDENTIALITY

Will participants be audiotaped, photographed or videotaped during this study? No

How will subject identity be protected?

The risk of breaching subject confidentiality will be minimized by identifying all participants by code numbers and by securing all data in locked files accessible only to research personnel. Neither the participant's name or nor any identifying information will be used in any publication or presentation resulting from this study.

Is there a Certificate of Confidentiality in place for this project? (If so, please provide a copy). No

12. CONFLICT OF INTEREST

(For information on disclosure reporting see: <http://www.udel.edu/research/preparing/conflict.html>)

Do you have a current conflict of interest disclosure form on file through UD Web forms?

Yes

Does this project involve a potential conflict of interest*? No

* As defined in the [University of Delaware's Policies and Procedures](#), a potential conflict of interest (COI) occurs when there is a divergence between an individual's private interests and his or her professional obligations, such that an independent observer might reasonably question whether the individual's professional judgment, commitment, actions, or decisions could be influenced by considerations of personal gain, financial or otherwise.

If yes, please describe the nature of the interest: not applicable

13. CONSENT and ASSENT

Consent forms will be used and are attached for review (see Consent Template under Forms and Templates in IRBNet)

Additionally, child assent forms will be used and are attached.

Waiver of Documentation of Consent (attach a consent script/information sheet with the signature block removed).

Waiver of Consent (Justify request for waiver)

14. Other IRB Approval

Has this protocol been submitted to any other IRBs? No

If so, please list along with protocol title, number, and expiration date. Not Applicable

15. Supporting Documentation

Please list all additional documents uploaded to IRBNet in support of this application.

- Informed Consent Form – clean copy and track changes
- Data Collection Form – On-site Evaluation (including updated Request for Participant Incentive form)
- Continuing Review Form
- Previously Approved Documents:
 - HIPAA Authorization Form
 - Advertisement
 - Recruitment Flier with Pull Tabs_Controls
 - Recruitment Flier with Pull Tabs_Amputees
 - Recruitment Print Advertisement
 - Consent to Contact Form
 - Other: Screening
 - Verbal Script for Recruitment
 - Telephone Demographics
 - Telephone Screen
 - Mailing Packet Questionnaires
 - Face Sheet
 - Demographics Sheet
 - Medical History Checklist
 - Medication Sheet
 - Activities Specific Balance Confidence Scale
 - Patient-Reported Outcomes Measurement Information System (PROMIS-29)
 - International Physical Activity Questionnaire (IPAQ)
 - Incidental and Planned Exercise Questionnaire-past week
 - Houghton Scale of Prosthetic Use
 - Directions to UDPT Clinic
 - Other: Participant Handouts
 - BP Screening
 - Physical Performance Testing_Controls
